## Standard Research Summary

### Purpose of the Study:

The objective of the study is to determine whether the beeswax-pine resin mixture used as part of the LowCostomy appliance as a buffer can be safely applied to human skin. "Safe" is defined as no greater external skin irritation or injury compared to standard commercially available ostomy appliance products such as the Hollister Adapt Seal barrier ring, used in a similar manner to the beeswax-pine resin buffer as part of the LowCostomy appliance (3). The hypothesis to be tested is that the beeswax-pine resin mixture is safe for topical application to human skin.

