#### **Design and Procedures:**

The purpose of this study is to examine the safety of the LowCostomy appliance's peristomal adhesive interface composed of a mix of beeswax and pine resin. Since this study is not directed at analyzing the efficacy of the entire LowCostomy system, only the beeswax mixture will be tested against test subjects' skin. Upon consultation with ostomy nurses, the peristomal skin was determined to be comparable to normal abdominal skin. Thus, rather than recruiting colostomy patients, the subject pool will include any willing healthy adults with age +/>>18 years (n=50). This subject pool must be heterogeneous in terms of ethnicity which ensures that a broad range of skin colors are being tested with the aim of removing bias toward a certain type or color of skin. The goal is to recruit 50% of subjects who self-identify as having a medium to dark skin tone and 50% who self-identify as having with a light skin tone. Subjects will be given \$50 as compensation.

Each study subject will be tested with two thin rings of the beeswax-pine resin formula—one being a domestic beeswax-pine sample while the other ring will be a Tanzanian beeswax-pine sample. Using both a domestic and international sample, we can test whether regional differences in these products might yield significantly different results. Such beeswax-pine samples will be tested alongside a control adhesive in the form of Hollister's AdaptTM Barrier Rings. The length of the study will be 7 days. The beeswax-pine ring will be created to match the dimensions of the control (width: 4.5 mm, outer diameter: 48 mm). The beeswax-pine buffer will be composed of the same beeswax-pine resin ratio that will be used in the LowCostomy appliance's overall design. Such tests will be performed on the subjects' abdomen. Prior to application, a licensed physician will record observations concerning the condition of the abdominal skin including color, odor, texture, and hygiene. Pictures will be obtained for documentation purposes as well using a Nikon D5600, 24.2M pixel camera. During picture taking we will limit identification by choosing an area of skin with limited identifying marks or tattoos. The camera will automatically date stamp the picture however, there will be no other identifiers captured. A single dedicated camera will be used for all photos. At the screening visit on Day 1, a member of the research team will obtain a current medication

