list and a medical history regarding known pre-existing skin conditions and history of skin reactions to elements of the study and control adhesive rings, to validate that there are no additional associated risks with participating in this study. If the area of application is too hairy to obtain a clear view of the skin, the healthcare professional will shave the pertinent area. The three areas of application will be marked with a medical marker to ensure even and consistent placement of the samples. A measurement device will be included in each picture for documentation and quantification of adverse skin reactions. The control ring will be applied according to the manufacturer's instructions; the beeswax-pine rings will be placed in a similar fashion but in addition, will need to be massaged against the skin to build friction and heat, allowing for a more effective adhesion. To fully seal the rings with the skin, Tegaderm will be placed over the rings, which allows the study subject to shower over the 7-day period with minimal interference with the study results. If the initial adhesives are not able to endure the full 7 days due to adhesive or application failure, such results will be noted and excluded from final analysis.

Each subsequent day after the initial placement of the samples, the subject will be asked to remove the tegaderm and the three adhesive rings briefly for less than 20 minutes, then promptly reapply in the exact same location with new tegaderm. The act of daily removal and reapplication of the samples will simulate

the typical routine of colostomy patients as they remove and reapply their ostomy products.

Twenty-four pieces of tegaderm will be provided per subject for the purpose of reapplying the samples. During the education session, subjects will be shown how to properly apply tegaderm over the three samples. Subject participation ends at Day 7.

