Photo documentation with the dedicated camera will occur on Day 1 at the initial screening visit as noted above, as well as Day 7. Photos will be collected by trained personnel in a private room without windows. A licensed physician will grade the blinded photos, indicating the appropriate level of skin irritation and rash by utilizing the Draize skin scoring system. Subjects will be given contact information to report any skin irritation or other adverse events during the 7-day trial period. Should a severe skin reaction occur, subjects will be directed to the licensed physician reviewer or a consult with a dermatologist. All subjects will record their experience through a RedCap survey which will include the 5D itch scale. After quantitative values have been assigned to each of the blinded photos, data visualizations will be created, and appropriate statistical analysis will be completed to evaluate for significant differences between each of the samples applied to subjects' skin.

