**Data Analysis and Statistical Considerations**

Data from subjects who successfully complete the seven-day study will be used for analysis. The photos from Day 1 and Day 7 will be reviewed by the licensed physician using the Draize skin scoring system. Subjects will fill out a survey of their experiences of wearing the beeswax-pine resin adhesive. The 5-D itch scale will be used to quantify subjective experiences. All photos included in the dataset will be blinded before a licensed physician quantitatively indicate the level of skin irritation. Only the data of subjects who completed data collection for the entire 7-day duration will have their results quantified. Statistical tests will be completed on the results to draw conclusion about whether the beeswax-pine resin samples, in comparison to our control, caused skin irritation.

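### The protocol does not say which product goes on which of the three abdominal areas, so a fixed or habitual layout would confound position with product

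*Protocol*

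**What the plan says.** The comparison is made within each subject. Under Design and Procedures, "Each study subject will be tested with two thin rings of the beeswax-pine resin formula", one domestic and one Tanzanian, and "Such beeswax-pine samples will be tested alongside a control adhesive in the form of Hollister's Adapt" barrier rings. On placement, "The three areas of application will be marked with a medical marker to ensure even and consistent placement of the samples". At the daily removal the subject is to take the rings off briefly, "then promptly reapply in the exact same location with new tegaderm", so a ring keeps its area all week.

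The three products are then compared. The analysis is to "evaluate for significant differences between each of the samples applied". The Data Analysis section asks "whether the beeswax-pine resin samples, in comparison to our control, caused skin irritation". With the two beeswax sources, "we can test whether regional differences in these products might yield significantly different results". Under Purpose of the Study, safe "is defined as no greater external skin irritation or injury compared to standard commercially available ostomy appliance products".

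No section says which product goes on which area, or that the layout is randomised, rotated or recorded. No section prescribes one layout for all subjects either.

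**The concern.** Using each subject as their own control removes differences between people. It does not remove differences between areas of the same abdomen. Those cancel only if each product sits at each area about equally often, and the protocol has no rule to bring that about. The phrase about even and consistent placement concerns marking the areas. Staff could read it as the same layout for everyone.

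Suppose one layout is used and one area is more prone to irritation than the other two, which are alike. Two of the three product comparisons are then biased, whichever ring sits there:

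- **Control at the worst area:** both beeswax v control comparisons are biased, and real harm can be hidden.
- **A beeswax ring at the worst area:** its comparison with control is biased towards a false harm signal, and the domestic v Tanzanian comparison is biased too.

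So at least one comparison that decides safety is always affected. Allotment happens on Day 1 and each ring then stays in place, so under one layout product and position coincide completely and no analysis can separate them.

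**Working it through.** **Inputs from the protocol.** Three products on three areas per subject, N = 50, comparison within subject. The protocol states no figure on this point, so there is none to reproduce.

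**Assumptions.** Irritation is scored yes/no and areas are independent. The rate is 5% at two areas and w = 7, 10, 15, 20 or 25% at the worst. The test is a two-sided exact McNemar test at 0.05, for one beeswax ring v control.

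**Formulas.** For a subject with rates p_B (beeswax) and p_C (control), the discordant probabilities are p10 = p_B(1 − p_C) and p01 = p_C(1 − p_B). The apparent excess is p10 − p01 = p_B − p_C. The rejection probability comes from exact enumeration of the discordant counts over 50 subjects.

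With δ = w − 5%, the bias in beeswax minus control when beeswax is the ring placed there is:

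- one layout: δ
- habit (there in 2/3 of subjects, each other ring in 1/6): δ(2/3 − 1/6) = δ/2
- no preference (1/3 each): 0, with a chance imbalance of SD δ√(2/(3n))

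**Example 1: no product effect, beeswax always at a 15% area.** p10 = 0.15 × 0.95 = 0.1425 and p01 = 0.05 × 0.85 = 0.0425. The apparent excess is 10 points, all of it from position. The false-positive rate is 25.7%.

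**Example 2: true excess of 20 points, control always at a 10% area.** Beeswax is at 25%. p10 = 0.25 × 0.90 = 0.225 and p01 = 0.10 × 0.75 = 0.075, so the apparent excess is 15 points and power is 40.7%. Without a position effect, p10 = 0.2375 and p01 = 0.0375, and power is 74.9%.

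| Rate at worst area | 7% | 10% | 15% | 20% | 25% |
|---|---|---|---|---|---|
| *False positives, no product effect (%)* | | | | | |
| Beeswax always there | 1.9 | 6.9 | 25.7 | 51.7 | 74.9 |
| Beeswax there in 2/3 | 1.2 | 2.7 | 6.8 | 12.9 | 20.5 |
| No preference | 1.0 | 1.4 | 1.8 | 2.1 | 2.3 |
| Six orders balanced | 1.0 | 1.3 | 1.6 | 1.7 | 1.6 |
| *Power, true 20-point excess (%)* | | | | | |
| Control always there | 60.8 | 40.7 | 16.9 | 5.6 | 1.5 |
| Control there in 2/3 | 67.0 | 55.3 | 38.2 | 24.7 | 15.2 |
| No preference | 72.9 | 70.2 | 66.2 | 62.5 | 59.1 |
| Six orders balanced | 73.0 | 70.3 | 66.3 | 62.7 | 59.3 |

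If the third ring always occupies the worst area, this one comparison is unaffected and its false-positive rate is 0.8%.

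**Effect of more subjects (worst area 15%; n = 50, 100, 200).** False positives are 25.7, 58.5 and 90.1% with one layout (bias stays 10 points), and 6.8, 16.3 and 33.7% with the 2/3 habit (bias stays 5 points). They are 1.8, 2.8 and 3.1% without preference, where the SD of chance imbalance shrinks: 10√(2/150) = 1.15 points, then 0.82 and 0.58.

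**Check on a graded score.** Take a paired test with n = 50 and a position effect d in SDs of the paired difference. Under one layout the rejection rate is about Φ(√50·d − 1.96) + Φ(−√50·d − 1.96). For d = 0.2, 0.3 and 0.5 this gives 29, 56 and 94%; simulation gives 28, 55 and 93%. With a layout randomised per subject it stays near 5% with bias near 0. With d = 0 both layouts give about 5%.

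**The case against.** The strongest reply is that this is a silence, not an error, and that harm needs two things at once: areas that differ in reactivity, and a systematic layout. The documents establish neither. All three areas are on the abdomen, and a layout list could exist in a working procedure that is not shown. The largest error rates need one area to irritate four or five times as often as the others. Against a haphazard layout the gain from balancing is almost nil: power differs by no more than about 0.3 point. The yes/no outcome, the test and the base rate are also assumptions, since the protocol names a graded Draize score and leaves the test open.

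Most of this stands, and it limits the weight of the point. It does not remove it. Which product goes on which site is a design matter that belongs in a protocol, and it cannot be left to the analysis plan because it is settled when the rings go on. A doubling from 5% to 10% at one area is enough to cut power from 75% to 41% if the control always sits there. Day 1 photographs can correct for differences visible before application, but not for differences in how areas react. Blinded grading does not help either, because the effect is on the skin itself.

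One practical objection also holds. Subjects reapply the rings themselves, and two of the rings share formula and dimensions, so individual orders need clear labelling of areas.

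**Conclusion.** The point holds. The protocol compares three products on three areas of each subject without any rule for allotting product to area, and it does not exclude one layout for all. The consequence is conditional. It is negligible if staff have no preference or if areas do not differ. Under a fixed layout it ranges from slight to severe: for worst-area rates of 7 to 25% against 5% elsewhere, false harm signals run from 2 to 75% when a beeswax ring sits there, and power for a true 20-point excess falls from 75% to between 61 and 1% when the control does. These figures rest on assumed rates, independent areas and an assumed test. The direction of the bias, and its failure to shrink with n, do not depend on those choices. It should be corrected before the first subject is enrolled, because under a single layout it cannot be corrected afterwards.

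**What to change.** In Design and Procedures, add that the six possible product-to-area orders are assigned from a pre-printed random list in blocks of six. With 50 = 6 × 8 + 2, each order is used by 8 subjects and two orders once more, so each product sits at each area in 16 to 18 subjects. Keep the existing rule that a ring stays at its area for the week. Enter the order on the case report form so that area can be included in the analysis.

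Two small additions help. Give the grader single-area photographs under random codes, without the order; with random orders, a physician who sees one subject in person learns only that subject's order. Label the areas, or give each subject a placement guide, so that daily reapplication follows the assigned order.

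The cost is a list, one form entry, photo coding and labels. No visits, staff or study products are added.

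### Skin results under a ring that fails before Day 7 are dropped, so the safety comparison rests on a subset selected after application

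*Protocol*

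**What the plan says.** Under Design and Procedures, the design is within-subject: "Each study subject will be tested with two thin rings of the beeswax-pine resin formula", one domestic and one Tanzanian, and "Such beeswax-pine samples will be tested alongside a control adhesive in the form of Hollister's Adapt" barrier rings on the same abdomen. Application is not the same for all products. The control follows the manufacturer's instructions, while the beeswax-pine rings "will need to be massaged against the skin to build friction and heat" so that they adhere better. Subjects take off and reapply all three rings every day.

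The same section then deals with rings that do not last the week: "due to adhesive or application failure, such results will be noted and excluded from final analysis". On the photographs it says: "Photo documentation with the dedicated camera will occur on Day 1 at the initial screening visit as noted above, as well as Day 7".

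The Data Analysis and Statistical Considerations section limits the analysis, in two separate sentences, to subjects who complete the week. The second reads: "Only the data of subjects who completed data collection for the entire 7-day duration will have their results quantified".

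Purpose of the Study defines safe as "no greater external skin irritation or injury compared to standard commercially available ostomy appliance products". Nothing in the protocol returns the skin result under a failed ring to any analysis; the failure is only noted.

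**The concern.** The question is what the mixture does to skin, not how long the ring stays on. A site whose ring fails on, say, Day 5 has been in contact with the mixture, and its condition is a safety observation. The rule discards that observation because of something that happens after application.

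Two features make this more than a loss of data. First, failure may differ by product: the test rings are a new formula, and only they need massaging on. Second, failure may be related to the state of the skin beneath. If both hold, the retained test and control sites are selected differently and their difference is biased, in a direction the documents do not fix. If failure is unrelated to irritation, there is no bias, but each exclusion still breaks at least one pair.

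The rule is also incomplete. It does not say whether one failed ring removes that ring or the whole subject, and the two readings give different analysis sets.

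**Working it through.** **Inputs.** From the protocol: 50 subjects (stated in one place as a minimum), three rings each, 7 days, photographs on Day 1 and Day 7. The protocol gives no failure rate, irritation rate or basis for the sample size, so there is no planned figure to reproduce. Every rate below is an assumption.

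**1. Pairs lost.** With the same independent failure probability p for each ring, expected test-control pairs per test product are 50(1−p)², and subjects with all three rings intact are 50(1−p)³. For precision, take irritation as a yes/no outcome at 20% on both products with independent sites. The 95% half-width for the paired difference is then 1.96·√(2·0.2·0.8/n), with n the number of pairs.

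| p | Pairs, exclusion by ring | Subjects, exclusion by subject | Half-width on the pairs (points) |
|---|---|---|---|
| 0 | 50 | 50 | 15.7 |
| 5% | 45.1 | 42.9 | – |
| 10% | 40.5 | 36.5 | 17.3 to 17.5 (n = 41, 40) |
| 20% | 32.0 | 25.6 | 19.6 |
| 30% | 24.5 | 17.1 | 22.2 to 22.6 (n = 25, 24) |

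With unequal failure, 20% for test rings and 5% for control, 50·0.80·0.95 = 38 pairs and 50·0.95·0.80² = 30.4 complete subjects remain.

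**2. Loss on a continuous score.** The detectable standardised paired difference at 80% power and two-sided 5% is (1.960+0.842)/√n. With 50 pairs this is 0.40. With 36 pairs (control failure 10%, test 20%: 50·0.9·0.8) it is 0.47, and power for 0.4 SD falls from 81% to 67%.

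**3. Selection.** Let true irritation be π, with failure f₁ at irritated sites and f₀ elsewhere. Irritation among retained rings is π(1−f₁)/[π(1−f₁)+(1−π)(1−f₀)]. For π = 20%:

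- f₁ = 30%, f₀ = 10%: 0.14/(0.14+0.72) = 16.3%
- f₁ = 10%, f₀ = 30%: 0.18/(0.18+0.56) = 24.3%
- f₁ = f₀: 20.0%, no bias

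These are rates for one product. For the comparison, with true irritation of 20% on both products:

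- If only the test ring has such a link, the apparent difference is 16.3 − 20.0 = −3.7 points or 24.3 − 20.0 = +4.3 points.
- If both products have the same link, the difference is zero.

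**4. What including failed sites does.** A failed site has less exposure and time to recover. Suppose irritation after 7-day wear is 20% on both products, failed sites show half of that on Day 7, and failure is 20% for test and 5% for control. Analysing all applied sites gives:

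- Test: 0.8·20% + 0.2·10% = 18.0%
- Control: 0.95·20% + 0.05·10% = 19.5%

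That is a tilt of 1.5 points towards the test ring.

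**The case against.** The strongest reply is that bias is possible but not shown. The exclusion is worded for mechanical failure, and the protocol covers stopping for a reaction separately. No text links loss of adhesion to skin condition, and a film dressing renewed daily may make failure rare. Seven-day wear also matches the stated objective of a one-week application, whereas sites exposed only briefly can dilute irritation and favour a claim of no greater irritation than control. Completing data collection is also not the same as keeping a ring on: a subject with a failed ring might still supply all seven days of data.

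The illustrations can be challenged too. Equal, independent failure leans towards heavy loss: with positive correlation within a subject, 20% failure leaves between 32 and 40 pairs. Independent sites overstate the interval: with a correlation of 0.5, the half-width is about 11 points at 50 pairs and 13 at 38. The Draize score is not binary, and 50 is a minimum. A bias of about 4 points lies well inside the sampling error.

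Much of this stands as a limit on size. The rate and direction are unknown, and dilution is real. It does not rescue the rule. A bias smaller than the interval half-width is still a bias, and it does not shrink as more subjects are recruited. The exposure argument supports showing the 7-day-wear set, but not showing it alone. Nor is this a detail left to the statistical analysis plan: the protocol itself sets the exclusion, and a later plan that kept these sites would contradict it.

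**Conclusion.** The concern holds. As written, the safety conclusion would be drawn from sites selected by an event after application, in a paired comparison where that event may differ between products. It is certain that the rule exists and that nothing offsets it; its effect is not certain.

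On the assumed rates, the loss runs from about 5 to 25 of 50 pairs per test product under ring-level exclusion, and from about 7 to 33 of 50 subjects under subject-level exclusion. The bias in the comparison runs from zero to about 4 points either way if only one product's failures depend on irritation. This should be corrected before analysis, because the outcome is largely obtainable from photographs already planned.

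**What to change.** In Design and Procedures, replace the exclusion sentence with:

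> Every site to which a ring was applied is graded on the Draize scale from the Day 7 photograph, or from a photograph taken when the subject stops early, and is included in the main comparison. The day and cause of failure are recorded for each ring, and failure rates are reported by product. An analysis limited to rings worn for all 7 days is presented alongside.

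In Data Analysis and Statistical Considerations, reword both completers-only sentences to agree, and add that a conclusion of no greater irritation must be supported by both analyses. That requirement guards against dilution in the all-applied set and selection in the 7-day-wear set. It also removes the ambiguity over whether a failed ring excludes the ring or the subject.

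The cost is rewording in two sections, a failure log per ring, one further analysis and a few unscheduled photographs for subjects who stop early. No rule on wear or stopping changes. The remaining drawback is that a Day 7 photograph of a site whose ring failed early also reflects recovery, so day of failure should be reported with the results.

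### Safety is defined as irritation no greater than the control ring, but the planned analysis looks for significant differences, and a non-significant difference cannot show that

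*Protocol*

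**What the plan says.** Under Purpose of the Study, the protocol says that safe "is defined as no greater external skin irritation or injury compared to standard commercially available ostomy appliance products", with a named barrier ring as the example. It continues: "The hypothesis to be tested is that the beeswax-pine resin mixture is safe for topical application to human skin". The claim to be shown is therefore directional: each beeswax-pine ring should be no worse than the control.

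Three later places describe comparisons.

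- **Design and Procedures, on the graded photographs:** "appropriate statistical analysis will be completed to evaluate for significant differences between each of the samples applied to" subjects' skin.
- **Design and Procedures, on the domestic and Tanzanian samples:** "we can test whether regional differences in these products might yield significantly different results".
- **Data Analysis and Statistical Considerations:** tests will be done to "draw conclusion about whether the beeswax-pine resin samples, in comparison to our control, caused skin irritation".

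Each subject wears all three rings, so every comparison is within subject. The sample size is 50 and only subjects who complete the seven days are analysed.

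**The concern.** The hypothesis and the stated aim of the analysis ask different questions. Looking for significant differences puts the burden of proof on showing that the rings differ. The claim of no greater irritation puts the burden on showing that any excess is small. A test of the first kind can overturn the safety claim if it finds a significant excess on beeswax, but it offers no way to support the claim when it finds none.

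The protocol does not say that non-significance will be read as safe. It does not describe any other route to that conclusion either. If the analysis follows the wording of Design and Procedures, a non-significant result could be reported as safe while the data still allow a sizeable excess of irritation over the control ring. The incentive also runs the wrong way: fewer subjects or noisier grading make the favourable-looking result more likely. This is the study's sole hypothesis, and it is a safety claim for a product meant for patients.

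**Working it through.** The protocol states no test, alpha, margin, SD or sample-size calculation, so there is no figure of its own to reproduce. What follows is illustration.

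**Inputs.** From the protocol: 50 subjects, within-subject comparison, completers only. Assumed: alpha 0.05; 40 analysed pairs as an example of data loss; for the yes/no case, a true 10% rate of reacting to beeswax only and no reactions to control only.

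**1. Graded score, paired t-test, in SDs of the within-subject difference.**

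The largest non-significant mean excess is t/√n. The one-sided 95% upper limit is the observed mean plus t(0.95, n−1)/√n.

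- n = 50: two-sided edge 2.010/√50 = 0.284; one-sided edge 1.677/√50 = 0.237. Upper limits at those edges: 0.284 + 0.237 = 0.521 and 2 × 0.237 = 0.474.
- n = 40: edges 2.023/√40 = 0.320 and 1.685/√40 = 0.266. Upper limits: 0.320 + 0.266 = 0.586 and 2 × 0.266 = 0.533.

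So a result called non-significant can be compatible with a true excess of about half an SD, and the limit widens as pairs are lost. From the noncentral t distribution, a true excess of 0.3 SD gives a non-significant two-sided result 45% of the time with 50 pairs and 54% with 40.

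**2. Yes/no reaction.**

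Let k be the number of subjects reacting to beeswax only, with none reacting to control only. The exact tests use 0.5^k (one-sided) or 2 × 0.5^k (two-sided). The chance of missing the excess is P(X ≤ k_min − 1) for X ~ Binomial(n, 0.10).

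| Test | k needed | Missed, n = 50 | Missed, n = 40 |
|---|---|---|---|
| One-sided t or asymptotic | 3 (p = .042) | 11% | 22% |
| Two-sided t | 4 (p = .044) | 25% | 42% |
| One-sided exact | 5 (0.5^5 = .031) | 43% | 63% |
| Two-sided exact | 6 (2 × 0.5^6 = .031) | 62% | 79% |

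**3. What particular results would leave open, n = 50.** The upper limit is Tango's one-sided 95% limit for a paired difference in proportions.

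- k = 2 (observed excess 4 points): p = .080 (one-sided t), .159 (two-sided t), .25 (one-sided exact), .50 (two-sided exact). None is significant. Upper limit 11.4 points (14.0 points for 2 of 40).
- k = 3 (observed excess 6 points): p = .042, .083, .125, .25 in the same order. Only the one-sided t is significant. Upper limit 14.1 points.

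**4. What 50 subjects can support if a margin is used.** Assume no true difference, one-sided alpha 0.025 and 80% power. The smallest margin that can be shown for one ring is then (1.960 + 0.842)/√n, which is 0.40 SD with 50 pairs and 0.44 SD with 40. A margin of 0.3 SD would need ((1.960 + 0.842)/0.3)² ≈ 88 subjects.

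**The case against.** Tests, null hypotheses and margins are commonly left to the SAP, which is not at hand. The protocol speaks only of appropriate analysis and statistical tests, so it does not rule out a no-worse-than test. It never says that non-significance means safe, and the Data Analysis section does describe a comparison with the control in terms that lean directional. A search for differences also has a proper place here: it suits the domestic-versus-Tanzanian question, and a significant excess on beeswax would refute safety. The illustrative figures rest on assumed inputs, and the miss rate at n = 50 runs from 11% to 62% depending on the test. A tight margin would not be achievable with 50 subjects, so rewording may cost more than it seems. Finally, this is a short study in healthy volunteers.

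Several of these points stand. The absence of a named test or margin is not in itself a fault, the inference from non-significance to safe is a risk and not a stated rule, and the figures show only the possible scale. The mismatch remains. The protocol does state an aim for the analysis of the graded photographs, and that aim does not match its own hypothesis. An SAP that faithfully carried out that sentence would inherit the problem, and the Data Analysis wording does not resolve it. The concern about margins is met by allowing the limit to be reported without a safety conclusion.

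**Conclusion.** The concern holds and must be fixed. As worded, the planned analysis can contradict the study's hypothesis but cannot establish it. This conclusion rests on the protocol's text and needs none of the assumed inputs.

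The size is illustrative. Under a paired t-test at alpha 0.05, a non-significant result with 50 pairs can leave an upper limit of 0.47 SD (one-sided test) to 0.52 SD (two-sided test), rising to 0.53 to 0.59 SD with 40. A true 10-point excess of reactions on beeswax would be missed in 11% to 62% of studies with 50 pairs and 22% to 79% with 40. Draize scores have few levels, so actual figures will differ.

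**What to change.** In Design and Procedures and in Data Analysis and Statistical Considerations, state the following.

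- Each beeswax ring is compared with the control ring on the same subject, using the paired difference in irritation and its upper confidence limit.
- No greater irritation is concluded only if, for both rings, that limit lies below a margin the sponsor justifies before data are seen.
- If no margin can be justified, the limit is reported and safety is not concluded from a non-significant test.
- The difference test is kept for the domestic-versus-Tanzanian comparison.
- The sample size stays at about 50, with its precision stated. For example, the one-sided 95% limit lies about 0.24 SD above the observed mean difference with 50 pairs and 0.27 SD with 40.

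The cost is rewording two sections and agreeing on a margin or on reporting the limit alone. No new measurements are needed, and n does not change. The downside is that safety becomes harder to claim: requiring both rings to succeed generally lowers power further, and if only a tight margin can be justified, 50 subjects may support no more than the reported limit. The exclusion of non-completers and failed rings is a separate issue that this change does not repair.
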